3.3 Study Procedures

Asthmatic patients will be tested at three different times:

- Day 1) ED visit
- Day 2) 48 hours post discharge
- Day 3) 14 days' post discharge

Day 1, participants will be recruited by the Emergency Medicine Research Group (EMeRG). They will receive standard emergency care for their asthma and once stabilized, informed consent will be obtained. A venous blood draw will be done prior to discharge. Once stabilized, the participant will be taken to a private area either within the ED department or [name]

lab in Clinical Sciences Building to ensure no interference with ED procedures. Applanation tonometry will be done to measure PWV, followed by FMD to determine endothelial function. **Day 2** the participant will return and the same assessments as Day 1 will be performed with the addition of spirometry according to standardized guidelines.¹⁸ Medication will not be withheld prior to this assessment. A Fitbit will be given along with instructions to wear the device for 7 days.

Day 3 will consist of the same measurements done in the ED for Day 1, with the addition of 2 quality of life questionnaires, the standardized Asthma Quality of Life Questionnaire (AQLQs) and the EQ-5D (5L), and the Asthma Control Questionnaire (ACQ), finishing with a full pulmonary function test including post-bronchodilator spirometry to evaluate for airway reversibility (i.e. asthma)¹⁹.

The participants are being tested 48 hours following the exacerbation to determine if systemic inflammation is further increased following an exacerbation, or if the exacerbation is when inflammation is at its peak. This will inform us on whether the exacerbation itself is the stimulus for increased systemic inflammation, or if it is a consequence of a stimulus in the days prior. The 14 day follow up was chosen based on the information that CRP is generally recovered to normal values after 14 days following stimulus,²⁰ as well, it is expected that lung function will have recovered 14 days following an exacerbation, as seen in other pulmonary disease exacerbations.²¹ Day 3 will tell us what average values for the participant would most likely be and allow us to compare the values obtained from the exacerbation against a personal reference value.

Stable asthmatics and healthy control participants will be tested at two different times:

- Day 1) date that participant is available for testing
- Day 2) 48 hours after Day 1

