Endothelial function - The endothelial function of the brachial artery will be evaluated after 10 minutes of rest in the supine position using ultrasound imaging (8L-RS 4.0-13.0MHz probe, Vivid q, GE Healthcare, Mississauga, ON). Baseline diameter of the brachial artery will be established, whereby the blood flow of the forearm will be occluded distal to the measuring site for the duration of 5 minutes. Upon release of the occlusion, the blood velocity and the brachial diameter will be monitored for 3 minutes, and later analyzed (Medical Imaging Applications, LLC, Coralville, IA, USA; EchoPAC PC software, version 110.x.x, GE Healthcare, Horten, Norway). Microvascular function will be evaluated as the velocity time integral-envelope of the first heartbeat of reactive hyperemia (VTI; m/s) and the velocity during reactive hyperemia (VRH) calculated as $VTI \times 60/HR$.²³ Shear stress during reactive hyperemia (SSRH) will subsequently then be calculated as $SSRH = 8 \times \text{flow} / \text{diameter}$ and as cumulative SSRH until the time of peak FMD%.^{24,25} FMD corrected for SSRH will be considered the main outcome for endothelial function in this study, and VRH and SSRH as indicators of microvascular function. Follow up tests will be conducted after a 12 hour fasting period when possible. Where applicable, the subjects will be asked to withhold any long-acting asthma medication for a minimum on 48 hours prior to the test, and short-acting asthma medications for 12 hours prior to the test.

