3.4.2 Statistical Methods

The mean differences in FMD, systemic inflammation, and arterial stiffness for ED visit compared to the control group will be evaluated using an unpaired t-test. A within-factors repeated measures analysis of variance (ANOVA) will evaluate the mean differences between each assessment day for the exacerbation group to assess change in endothelial function during exacerbation as well as the recovery period. A similar evaluation will be used for arterial stiffness and systemic inflammation/immune response. A one-way analysis of covariance (ANCOVA) will be used to correct for shear rate in FMD for all groups, with both values being reported. An α -level of 0.05 will be used as the significance level for all statistical analysis, and all results will be reported as mean \pm standard deviation unless indicated otherwise.

4 Data Handling and Record Keeping

Data to be collected:

Outcome variables:

Endothelial function

Source of the data: Flow-mediated dilation test (see *measurement, endothelial function* above).

Time point for collection: Collected as the last assessment during the ED visit. For the 2 follow up visits, FMD will be done after arterial stiffness and prior to blood draw.

Who will collect the data: All data will be collected by trained research staff associated with the study.

Why the data is being collected: To evaluate the influence of acute asthma exacerbation on vascular health.

Is the data from a standardized tool: Yes.

What form will the data will take (e.g. binary, continuous (numeric), time to event): Continuous.

Arterial stiffness

Source of the data: pulse wave velocity test (see *measurements, arterial stiffness* above).

Time point for collection: At the ED, arterial stiffness will be collected after blood draw and prior to endothelial function. At the follow up visits, it will be collects as the primary assessment.

Who will collect the data: All data will be collected by trained research staff associated with the study.

Why the data is being collected: To evaluate the influence of acute asthma exacerbation on vascular health.

Is the data from a standardized tool: Yes.

What form will the data will take (e.g. binary, continuous (numeric), time to event): Continuous.

Systemic inflammation and immune response

Source of the data: Venous blood samples (see *measurements, systemic inflammation and immune response* above).

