Time point for collection: At ED, blood will be collected as the primary assessment. At follow up visits, it will be collected as the final assessment.

Who will collect the data: All data will be collected by trained research staff associated with the study.

Why the data is being collected: To evaluate changes in systemic inflammatory levels and immune response throughout the study.

Is the data from a standardized tool: Yes.

What form will the data will take (e.g. binary, continuous (numeric), time to event): Continuous.

Explanatory variables and potential confounding variables:

Participant demographics, health history, and current status

Source of the data: interview with the participant as well as medical chart and ED physician. (see appendix 5)

Time point for collection: in the ED once hemodynamically stable and while receiving treatment. At follow up visits, additional information will be collected prior to assessments.

Who will collect the data: All data will be collected by trained research staff associated with the study.

Why the data is being collected: To ensure subject meet the inclusion/exclusion requirements, to obtain information on potential confounding variables, and to obtain general sample characteristics.

Is the data from a standardized tool: No, demographics will be collected according to the data collection document provided.

What form will the data will take (e.g. binary, continuous (numeric), time to event): Nominal, continuous or ordinal.

Perceived level of control and quality of life

Source of the data: The asthma control questionnaire (see appendix 1), asthma quality of life questionnaire (see appendix 2), and EQ-5D (see appendix 3).

Time point for collection: at 14 day post-discharge follow up.

Who will collect the data: All data will be collected by trained research staff associated with the study.

Why the data is being collected: To evaluate the current levels of perceived asthma control, disease specific quality of life and generalized quality of life.

Is the data from a standardized tool: Yes.

What form will the data will take (e.g. binary, continuous (numeric), time to event): Continuous.

Lung function

Source of the data: Pulmonary function test (see *measurements, pulmonary function* above)

Time point for collection: during a pre-test session, and at each baseline time-point.

Who will collect the data: All data will be collected by trained research staff associated with the study.

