 Collector Initiate Study ID #

Respiratory Discharge Medication (check all that apply)	Prescription Status	Daily dose prescribed
Short acting beta2 agonists  Ventolin  Advair  Advair  Advair  Other _____	 Existing  New	 prn  daily
Long acting beta agonists  Advair  Advair  Advair  Advair  Other _____	 Existing  New	 prn  daily
Inhaled corticosteroid  Cort  Cort  Cort  Cort  Cort  Other _____	 Existing  New	Breakdown: ____ Puff(s)  day  bid  qd  qd Daily total: _____ mcg
Combinations  Symbicort  Advair  Advair  Advair  Advair  Other _____	 Existing  New	Breakdown: ____ Puff(s)  day  bid  qd  qd Daily total: _____ mcg
Corticosteroids  Prednisone  Dexamethasone  Other _____	 Existing  New	Daily total: ____ mgs  PO  IV for ____ days

Source Documentation Version Date: June 27th 2018

Asthma Form
 Collector Initiate Study ID #

Antibiotics Specify _____	Breakdown: ____ mgs  day  bid  qd  qd
 Existing  New	Daily total: ____ mgs  PO  IV for ____ days

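### A fall in inflammation between the ED visit and 48 hours cannot show whether the exacerbation was the stimulus, because treatment spans the same interval and enters no analysis

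*Combined protocol and SAP*

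**What the plan says.** Section 3.3 explains why patients return 48 hours after discharge: to see whether inflammation rises further or is already at its highest during the exacerbation. It then states the conclusion to be drawn: "This will inform us on whether the exacerbation itself is the stimulus for increased systemic inflammation", the alternative being that the exacerbation follows from something that happened in the preceding days. For the 14-day visit it says "Day 3 will tell us what average values for the participant would most likely be", so that visit serves as the patient's own reference.

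On the order of events at the first visit, section 3.3 says "They will receive standard emergency care for their asthma and once stabilized, informed consent will be obtained". The blood draw, PWV and FMD come after that.

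Section 3.4.2 gives the analysis: "A within-factors repeated measures analysis of variance (ANOVA) will evaluate the mean differences between each assessment day for the exacerbation group". It reads the result as change during the exacerbation and the recovery. The section's other methods are an unpaired t-test at the ED visit and an ANCOVA for shear rate in FMD. Waist circumference is mentioned in section 3.3 as a possible covariate. No treatment variable appears in any model.

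Treatment is nevertheless recorded. Section 4 says that one purpose of the participant data is "to obtain information on potential confounding variables". Appendix 5 has ED fields for inhaled beta-agonist, inhaled anticholinergic and corticosteroid (including oral and intravenous agents). It also has a block headed "Respiratory Discharge Medication (check all that apply", in which corticosteroids are marked existing or new, with daily dose and number of days.

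**The concern.** Three things happen over the same days: the exacerbation runs its natural course, ED treatment takes effect, and discharge treatment begins. An analysis with visit as its only factor estimates their sum. Section 3.3 attributes that sum to the first of them.

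At stake is the mechanistic conclusion the 48-hour visit was added to support. If CRP or another marker falls, the plan as written would read this as inflammation having peaked at the exacerbation, although treatment alone could produce the same fall. The changes in FMD and PWV to 48 hours and Day 14 carry the same mixture when they are presented as recovery.

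**Working it through.** **1. The plan's own figures.** The documents give no figure on this point. The 36 per group in section 3.4.1 (44 with the 8 added for dropout) concerns a between-group difference in VTI. It cannot be reproduced, because neither the SD nor the power is stated. I use 36 only as the planned number of evaluable patients.

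**2. What lies between the measurements.**

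| Time | Measurement | Treatment the documents place there |
|---|---|---|
| ED | Blood, PWV, FMD | Standard ED care beforehand (3.3); corticosteroid fields (Appendix 5) |
| 48 hours | Same, plus spirometry | Discharge prescriptions, new or existing (Appendix 5) |
| Day 14 | Same, plus full PFT and questionnaires | Any corticosteroid course recorded in days (Appendix 5) |

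**3. What each result at 48 hours would mean.** Observed change = natural change + treatment change. Assume that treatment lowers the marker. The documents do not state the direction for any marker.

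- Fall: fits a natural peak at the exacerbation. It also fits no natural change, or even a natural rise, outweighed by treatment. It does not discriminate.
- No change: fits a stable marker or a natural rise masked by treatment.
- Rise: the natural change must exceed the treatment change, so it remains informative.

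**4. Whether the controls separate the two.** Stable asthmatic and healthy controls are seen twice, 48 hours apart, to measure natural fluctuation. They receive no ED treatment and have no Day 14 visit, so subtracting their change does not remove a treatment effect.

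**5. How the unadjusted comparison behaves (illustration; all shifts assumed).** Take natural change as zero and a treatment shift of δ SDs of the paired difference. For a two-sided 5% paired t-test (the plan does not state sidedness), the statistic is noncentral t with n − 1 degrees of freedom and noncentrality δ√n. With n = 36 the noncentrality is 6δ.

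| δ | 6δ | Probability of declaring a change |
|---|---|---|
| 0.1 | 0.6 | 9% |
| 0.2 | 1.2 | 22% |
| 0.3 | 1.8 | 42% |
| 0.5 | 3.0 | 83% |

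This is a single pairwise contrast, a simplification of the three-visit ANOVA.

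**6. What the recorded treatment data could add.** Compare change between patients with and without corticosteroid at 80% power and two-sided 5% (normal approximation). The detectable difference is (1.960 + 0.842) × √(1/n₁ + 1/n₀), in SDs of the change. The treated share is assumed.

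| Share treated | n₁ / n₀ | Detectable difference |
|---|---|---|
| 50% | 18 / 18 | 2.802 × 0.333 = 0.93 SD |
| 80% | 28.8 / 7.2 | 2.802 × 0.417 = 1.17 SD |
| 90% | 32.4 / 3.6 | 2.802 × 0.556 = 1.56 SD |
| 95% | 34.2 / 1.8 | 2.802 × 0.765 = 2.14 SD |

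The plain within-group change is detectable at 2.802/6 = 0.47 SD. The subgroup comparison is therefore a coarse check, and it has nothing to say if almost everyone is treated.

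**7. Drug exposure at follow-up.** Under the Day 2 procedures, section 3.3 says "Medication will not be withheld prior to this assessment". Under the endothelial function measurement, it says "the subjects will be asked to withhold any long-acting asthma medication for a minimum on 48 hours prior to the test", with 12 hours for short-acting drugs. The first statement follows the mention of spirometry and may be meant for that test alone, but FMD is done at the same visit. For a visit 48 hours after discharge, a minimum of 48 hours covers the whole interval since discharge (48 − 48 = 0). Until the statements are reconciled, drug exposure at the 48-hour tests is undefined.

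**The case against.** The best defence is that the course under usual care is a legitimate target. The objectives in section 2 are only to examine vascular function and inflammation in a naturally occurring exacerbation, and section 3.4.2 speaks of recovery, not of untreated recovery. The sentence about the stimulus justifies a visit time and is not a hypothesis. Much of this stands: the repeated-measures analysis is sound as a description. It does not rescue the sentence itself, which states a causal reading that a description of treated patients cannot give.

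It can also be said that adjustment would not solve the problem, because treatment tracks severity and may be nearly universal. That stands as well, and is why the wording has to change whatever the sensitivity analysis shows.

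A reader might infer that Appendix 5 already allows a full adjustment for cumulative dose and time since last dose. The form does not show this. As far as it is legible, it takes the first treatment, the first corticosteroid given when there was more than one dose, and the dose prescribed at discharge. No last-dose time and no record of doses taken after discharge is visible; section 4 promises only unspecified further information at follow-up.

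A reader might also want Day 14 checked against the stable asthma group. That would not validate a reference personal to each patient. Section 3.1.1 states matching only for healthy controls, and the stable group may include unconfirmed asthma, so neither a difference nor its absence would establish recovery. The Day 14 ACQ and full PFT bear on recovery more directly.

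**Conclusion.** The point holds in a limited form. If values fall at 48 hours, the planned analysis cannot separate natural course from treatment, and the conclusion section 3.3 would draw about the stimulus is not supported. The same limit applies to reading the FMD and PWV changes as recovery from the exacerbation alone.

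A reader might go further and infer that the 48-hour comparison is worthless, or that a percentage bias can be attached to it. The documents support neither. A rise would keep its meaning for any marker that treatment lowers. With no treated share and no drug effect given, any percentage would merely return whatever was assumed; the probabilities in the working show only how the test behaves over a range of assumed shifts.

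The conclusion rests on one inference: that treatment differs over the interval. The order of events in section 3.3 and the ED and discharge fields in Appendix 5 support it, but the documents do not say how many patients are treated. This should be corrected before analysis. It does not put the data collection in question.

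**What to change.** - **Section 3.3, interpretation.** Describe the 48-hour and Day 14 changes as the course of a treated exacerbation. Remove the sentence about the stimulus, or restrict it so that no such conclusion is drawn when values fall.
- **Section 3.4.2.** Pre-specify, as a sensitivity analysis, the visit changes in biomarkers, FMD and PWV by recorded systemic corticosteroid use (given in the ED, yes or no; prescribed at discharge, yes or no), with confidence intervals. State that treatment tracks severity and that the analysis is uninformative if nearly all patients are treated.
- **Section 3.3, medication before follow-up tests.** Reconcile the statement under the Day 2 procedures with the one under the endothelial function measurement, and say which tests and visits each covers.

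The first two changes need only wording and one additional table from fields already on the form. The price is small subgroups: crossing the two corticosteroid fields gives four cells, or 36/4 = 9 patients each even if evenly filled. Intervals will be wide and the estimates remain observational.

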3.1 Study Design

3.1.1 General Design

This study is a cohort study utilizing a repeated measure design. Asthmatic patients will be tested at 3 different time points:

- At the emergency department
- 48 hours following discharge
- 14 days following discharge

Stable asthmatic and non-asthmatic controls will be tested at two time points:

- Day 1
- 48 hours following Day 1

Vascular parameters such as flow mediated dilation (FMD; endothelial function) and pulse wave velocity (PWV; arterial stiffness) will be evaluated at each time point to assess vascular function. Blood samples will be obtained for analysis of systemic inflammatory response and immune response at each time point.

Participants will also be given Fitbit activity monitors for 7 days of monitoring, perform a full pulmonary function test (PFT) and complete 3 questionnaires; Asthma Control Questionnaire (ACQ), Asthma Quality of Life Questionnaire (AQLQ), and EQ-5D.

(A) Cohort studies

Definition of study groups:

Individuals experiencing an asthma exacerbation will be identified at the University of Alberta Emergency Department (ED). They will be recruited based on asthma being the primary physician diagnosis in the ED, with asthma being confirmed at a follow up visit using spirometry.

Stable asthmatic controls will be recruited from the general populations, as well as two local pulmonary clinics: The Lung Health Clinic, Edmonton, AB; and the University Lung Clinic, Edmonton, AB. These participants will be recruited if they have indicated they have been diagnosed with asthma. Both confirmed and unconfirmed asthmatics will be eligible.

Healthy controls will be recruited from the general population. They will be age-, sex, and BMI matched to the exacerbation group.

Blinding and avoiding bias:

Due to the nature of the study, blinding will not be applicable.

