Controls are being tested at two times to determine the degree of natural fluctuations in endothelial function, arterial stiffness, and systemic inflammation in healthy adults.

Measurements

Waist Circumference – Using a fabric tape measure, waist circumference will be measured at the level of the last rib to the nearest 0.1 cm after a normal expiration.¹⁷ This will be used as a measure of adiposity and will potentially be used as a covariate during statistical analysis.

Arterial stiffness - Arterial stiffness will be evaluated using pulse wave velocity (PWV) between the carotid and femoral arteries. After 10 minutes of resting in a dark, quiet room in the supine position, cPWV and pPWV will be recorded using applanation tonometry (Complior, Alam Medical, Saint Quentin Fallavier, France). A series of 10 consecutive beats will be taken with a minimum quality of 85%. The distance between the carotid and femoral artery, as well as the carotid and radial artery will be recorded in mm. PWV will be measured prior to FMD and blood collection, and will be taken on all 3 days of assessments. PWV is expressed as m/s and is calculated as $PWV = L/\Delta t$, with L being the distance between the two points and Δt being the time it takes for the pulse to get from site 1 to site 2.²²

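### The controls' 48-hour visit is scheduled to measure natural fluctuation, but no planned analysis estimates their change or compares it with the patients' change

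*Combined protocol and SAP*

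**What the plan says.** Under 3.1.1 and 3.3, exacerbation patients are measured in the ED and then 48 hours and 14 days after discharge. For the other two groups, "Stable asthmatics and healthy control participants will be tested at two different times": Day 1 and "48 hours following Day 1". Section 3.3 gives a single purpose for the second control visit: "Controls are being tested at two times to determine the degree of natural fluctuations in endothelial function, arterial stiffness, and systemic inflammation in healthy adults".

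Section 3.4.2 then plans three analyses:

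- A comparison of FMD, inflammation and stiffness "for ED visit compared to the control group will be evaluated using an unpaired t-test". The control visit is not named.
- "A within-factors repeated measures analysis of variance (ANOVA) will evaluate the mean differences between each assessment day for the exacerbation group". Its stated aim is "to assess change in endothelial function during exacerbation as well as the recovery period". For the other outcomes, "A similar evaluation will be used for arterial stiffness and systemic inflammation/immune response".
- A one-way ANCOVA in all groups that adjusts FMD for shear rate.

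Section 3.3 also explains what the patients' later visits are for. The 48-hour visit should show whether inflammation rises further after the attack or is already at its peak. The 14-day visit supplies each patient's own reference value.

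**The concern.** The study pays for a second visit in both control groups, up to 2 x 44 = 88 visits, so that ordinary movement in the outcomes is known. The statistical section never puts that knowledge to use. The only analysis over time is confined to the exacerbation group, so its null hypothesis is no change at all. The question of interest is whether the change exceeds what people without an exacerbation show between two visits 48 hours apart.

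Two conclusions depend on this: change in endothelial function during exacerbation and recovery (3.4.2), and the timing of the inflammatory peak (3.3). If FMD or CRP moves between a first and second test for reasons unrelated to asthma, such as familiarity with cuff occlusion or less anxiety, the planned ANOVA will credit that movement to the exacerbation or to recovery from it.

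**Working it through.** **Step 1. Does any planned analysis use the controls' change?**

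| Analysis in 3.4.2 | Groups | Visit factor | Estimates control change? |
|---|---|---|---|
| Unpaired t-test | ED visit against controls | none; control visit unnamed | No, whether it uses Day 1, 48 hours or their average |
| Repeated-measures ANOVA | exacerbation only | ED, 48 hours, 14 days | No |
| One-way ANCOVA for shear rate | all | none | No |

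The sentence extending the ANOVA to stiffness and inflammation adds outcomes, not groups. Nowhere is there a group-by-visit term, a difference in change or a repeatability estimate.

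**Step 2. Inputs.** From 3.4.1: 36 completers per group, and 36 + 8 = 44 recruited. From 3.4.2: alpha 0.05, taken here as two-sided because sidedness is not stated. The sample size itself is justified by a 13% between-group difference in VTI, with no SD or power given. It cannot be reproduced, and only n = 36 is used below. The drift sizes are assumptions; the documents give none.

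**Step 3. Test of change against zero, with no true effect.** A paired t-test of ED against 48 hours stands in for that contrast of the ANOVA. Let d be the mean drift in SDs of the individual change. The noncentrality is d x sqrt(36) = 6d, with 35 degrees of freedom and critical value 2.030.

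| d | noncentrality | P(significant) |
|---|---|---|
| 0 | 0 | 0.05 |
| 0.2 | 1.2 | 0.215 |
| 0.3 | 1.8 | 0.417 |
| 0.4 | 2.4 | 0.646 |

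The drift can instead be expressed in between-person SDs, with an assumed visit-to-visit correlation rho. The SD of change is then SD x sqrt(2(1 - rho)). For rho from 0.3 to 0.8, a drift of 0.2 SD is significant in 17% to 45% of studies, and a drift of 0.3 SD in 32% to 79%.

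**Step 4. Difference in change, 36 against 36.** The noncentrality is (difference in drift) x sqrt(36/2), with 70 degrees of freedom and critical value 1.994.

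- If controls share the drift fully, the difference is 0 and the rejection probability is 0.05.
- If the drift occurs only in the exacerbation group, the noncentralities at 0.2, 0.3 and 0.4 SD are 0.85, 1.27 and 1.70, and the rejection probabilities are 0.13, 0.24 and 0.39.

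**Step 5. Price in precision.** At 80% power and two-sided 0.05, the detectable change is 0.480 SD of change for one group of 36 and 0.670 for 36 against 36, assuming the same change variance in every group. In between-person SDs (normal approximation), the detectable difference in change is (1.960 + 0.842) x sqrt(2/36) x sqrt(2(1 - rho)), which gives 0.78, 0.66, 0.51 and 0.42 for rho = 0.3, 0.5, 0.7 and 0.8.

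**The case against.** The strongest reply is that the controlled contrast would not cure most of what could go wrong. Controls come on a day that suits them. They cannot share regression to the mean in people enrolled at an acute moment, the move from ED to laboratory, or ED treatment before the first measurement. Nor do they share the patients' change in blood-draw order (first in the ED, last at follow-up, section 4) or their change from an unplanned ED visit to a follow-up with fasting where possible (3.3). This stands: a reader might infer that subtracting the control change restores the 5% error rate, and step 4 shows that it does so only for drift the groups share. Return from the exacerbation state is, moreover, partly what the ANOVA is meant to measure, so it should not all be called artefact.

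Two other strong readings also go beyond the text. A reader might infer that the second control visit is used nowhere. The t-test names no control visit, so the 48-hour values could enter it; what is missing is any estimate of the controls' change. A reader might also infer that the patients' values have no comparator. The 14-day visit provides a personal one, though it does not measure fluctuation, and with no 14-day control visit that contrast is itself uncontrolled.

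Finally, the two 48-hour intervals differ: the patients' runs from discharge and the controls' from Day 1, and the gap between ED measurement and discharge is not given. None of these points supplies the missing analysis.

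**Conclusion.** The gap is real and limited. The plan states a purpose for the controls' second visit and contains no analysis that serves it. As planned, a significant ED-to-48-hour change cannot be distinguished from ordinary fluctuation and repeat-test effects. The ED-versus-control comparison is not undermined by this, although the control visit it uses needs naming.

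The probabilities of 0.22, 0.42 and 0.65 show how sensitive the planned test is to drifts of 0.2, 0.3 and 0.4 SD of change. They rest on assumed drifts, 36 completers and a two-sided paired contrast, and they do not predict how much drift will occur. The plan should be amended, because the claims about change over time depend on this contrast and the data needed are already scheduled.

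**What to change.** In 3.4.2:

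1. Add a group-by-visit model with two visits per group: ED and 48 hours after discharge for the exacerbation group, and Day 1 and 48 hours for the stable-asthma and healthy groups. Report the difference in change between the exacerbation group and each control group for FMD, PWV and CRP.
2. Report the controls' within-person SD over 48 hours, which is the quantity their second visit was scheduled to provide.
3. Name the control visit used in the unpaired t-test.
4. Keep the three-visit ANOVA within the exacerbation group, and label the 14-day contrast as uncontrolled.
5. State that subtracting the control change removes only shared effects, not regression to the mean, change of setting, ED treatment, blood-draw order or fasting differences, and that the groups' intervals start from different points.

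The cost is SAP wording and one further model, with no added visits. The statistical price is the rise in detectable change from about 0.48 to about 0.67 SD of change, under the assumptions in step 5. The within-group ANOVA remains available alongside it.
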